16.6.1. Blinded ANCOVA analysis

To analyse the four endpoints above, an ANCOVA approach will be used with a fixed factor for reversibility strata, and the baseline result as a covariate. Any missing data at Visit 6/Week 4 will be imputed using the LOCF method described in Section 16.4.

The ANCOVA model will use the square root of mean square error to estimate the blinded standard deviation.

Document: ...\\Verona_Pharma\\RPL554\\BZA48916\\Biostatistics\\Documentation\\SAP\\Verona CO-205 SAP v1.0

Author: [REDACTED] Version Number: V1.0

Version Date: 05DEC2019

Template No.: CS_TP_BS016 Revision 5

Reference: CS_WI_BS005

Effective Date: 01Apr2018

16.6.2. Blinded MMRM analysis

To analyse the change from baseline FEV₁ to peak FEV₁, an MMRM approach will be used with a fixed factor for visit, patient as a random effect, and the baseline result as a covariate. An unstructured covariance structure will be used to model the within-patient errors. If the model does not converge a compound symmetry covariance structure will be used. Kenward-Roger method will be used to estimate the model degrees of freedom.

Sample size calculation is based on the number of patients with available data at Visit 6/week 4 included in the analysis, therefore any assessment of sample size based on MMRM should also consider the drop-out rate observed in the study.

The MMRM model will use the square root of variance representing Visit 6/Week 4 taken from variance-covariance matrix to estimate the blinded standard deviation.

17. SAFETY OUTCOMES

All outputs for safety outcomes will be based on the SAF set, unless otherwise stated.

There will be no statistical comparisons between the treatment groups for safety data, unless otherwise specified within the relevant section.

17.1. Adverse Events

AEs will be listed for ENR set, with patients classified according to actual treatment received, and summarized for SAF set.

AEs will be coded using the MedDRA central coding dictionary, Version 22.0.

Treatment emergent adverse events (TEAEs) are defined as all AEs which start after the first dose of study treatment or start prior to first dose of study treatment and worsen, based on the investigator's assessment of severity, on or after first dose of study treatment.

Non-treatment emergent adverse events (non-TEAEs) are defined as AEs that start prior to first dose of study treatment and end prior to first dose of study treatment, or do not worsen, based on the investigator's assessment of severity, on or after first dose of study treatment.

In the case where it is not possible to define an AE as treatment emergent or not, the AE will be classified by the worst case; i.e. treatment emergent.

If any AE records contain only partial dates, these will be handled by imputation, as described in the Appendix 2.

Document: ...\\Verona_Pharma\\RPL554\\BZA48916\\Biostatistics\\Documentation\\SAP\\Verona CO-205 SAP v1.0

Author: [REDACTED] Version Number: V1.0

Version Date: 05DEC2019

Template No.: CS_TP_BS016 Revision 5

Reference: CS_WI_BS005

Effective Date: 01Apr2018

An overall summary of the number of patients with at least one event in each of the categories listed below will be provided as specified in the templates. In addition, the number of patients with each of the following AE events will be presented by SOC and PT and summarized by treatment group:

- TEAE
- TEAEs leading to discontinuation of study treatment
- TEAEs causally related to study treatment
- TEAEs by maximum severity
- Serious TEAEs
- Serious TEAEs causally related to study treatment
- Serious TEAEs by maximum severity
- Serious TEAEs leading to discontinuation of study treatment
- TEAEs with an outcome of death

AEs will be identified by using the 'Adverse Events' page of the eCRF. Listings will include TEAEs and Non-TEAEs.

17.1.1. Severity

Severity is classed as mild/ moderate/ severe. TEAEs starting after the first dose of study treatment with a missing severity will be classified as severe. If patient reports a TEAE more than once within that SOC/ PT, the AE with the worst-case severity will be used in the corresponding severity summaries.

17.2. Laboratory Evaluations

Results from the central laboratory will be included in the reporting of this study for Hematology, Blood Chemistry, Urinalysis and Viral Serology. Measurements and timepoints for each laboratory assessment can be found in Table 3.

Presentations will use standard international (SI) Units.

The handling of re-tests and unscheduled measurements is detailed in Section 6.3.

Document: ...\\Verona_Pharma\\RPL554\\BZA48916\\Biostatistics\\Documentation\\SAP\\Verona CO-205 SAP v1.0

Author: [REDACTED] Version Number: V1.0

Version Date: 05DEC2019

Template No.: CS_TP_BS016 Revision 5

Reference: CS_WI_BS005

Effective Date: 01Apr2018

Table 3: Laboratory Assessments

Laboratory Assessment	Measurements	Time points
Hematology	hemoglobin, hematocrit, total white cell count, leukocyte differential count and platelet count	Screening and at the End of Study visit
Blood Chemistry	creatinine, total bilirubin, alkaline phosphatase, aspartate aminotransferase, alanine transaminase, gamma-glutamyl transferase, lactate dehydrogenase, creatine kinase, thyroid stimulating hormone*, triiodothyronine and thyroxine*, glucose, potassium, sodium and calcium	Screening and at the End of Study visit
Urinalysis	leukocytes, blood, ketones, bilirubin, urobilinogen, protein and glucose	Screening and at the End of Study visit
Viral Serology	human immunodeficiency virus, hepatitis B and hepatitis C serology	Screening

*Will only be measured at Screening.

The following summaries will be provided for laboratory data (Hematology, Blood Chemistry and Urinalysis), summarised by treatment group:

- Shift tables representing changes from Low/Normal/High, determined by reference normal range.
- Listings of patients meeting markedly abnormal criteria after the first dose

Change from baseline table by post-dose time-point of collection for continuous variables will be summarised by treatment group for Hematology and Blood Chemistry.

Viral Serology data will be listed.

17.2.1. Laboratory Markedly Abnormal Criteria

Markedly abnormal quantitative safety (and other) laboratory assessments will be identified in accordance with the predefined markedly abnormal criteria as presented in Table 4. All laboratory parameter results will be listed.

Table 4: Markedly abnormal ranges for clinical laboratory parameters

Parameter	Markedly Abnormally High Criteria
Alanine Amino Transferase (ALT)	>3 times Upper Limit of Normal Range
Alkaline Phosphatase	>3 times Upper Limit of Normal Range
Aspartate Amino Transferase (AST)	>3 times Upper Limit of Normal Range
Creatinine	>221 µmol/L
Gamma Glutamyl Transferase (GGT)	>3 times Upper Limit of Normal Range
Total Bilirubin	>3 times Upper Limit of Normal Range

17.3. ECG Evaluations

12-lead ECG will be centrally collected at Screening, pre-dose and 2 hours post-dose for Day 1, Weeks 1 and 4. Details regarding retests and unscheduled measurements can be found in Section 6.3.

The following ECG parameters will be reported for this study:

- Heart Rate (bpm)
- PR Interval (msec)
- RR Interval (msec) [derived]
- QRS Interval (msec)
- QT Interval (msec)
- QTcF Interval (msec) [derived]
- Overall assessment of ECG (Investigator's judgment):
 - Normal
 - Abnormal, Clinically Significant (ACS)
 - Abnormal, Not Clinically Significant (ANCS)

The following summaries will be provided for ECG data, summarised by treatment group:

- Change from baseline table by post-dose time-point of collection for continuous variables
- Shift tables representing changes from Normal/ ACS/ ANCS, using Vendor's criteria
- Listings of patients meeting markedly abnormal criteria after the first dose

17.3.1. ECG Specific Derivations

The following ECG parameters are derived in the eCRF using the formulae shown below. To derive them, the parameters used will need to be collected at the same assessment, as per the "ECG" page of the eCRF.

- RR Interval

Document: ...\\Verona_Pharma\\RPL554\\BZA48916\\Biostatistics\\Documentation\\SAP\\Verona CO-205 SAP v1.0

Author: [REDACTED] Version Number: V1.0

Version Date: 05DEC2019

Template No.: CS_TP_BS016 Revision 5

Reference: CS_WI_BS005

Effective Date: 01Apr2018

- $RR \text{ (msec)} = 1000 * \frac{60}{HR \text{ (bpm)}}$
- Fridericia's Correction (msec)
 - $QTcF \text{ (msec)} = \frac{QT \text{ (ms)}}{\sqrt[3]{RR \frac{ms}{1000}}}$

17.4. Vital Signs

The following Vital Signs measurements will be reported for this study:

- Supine Systolic Blood Pressure (mmHg)
- Supine Diastolic Blood Pressure (mmHg)
- Supine Pulse Rate (bpm)
- Body weight (kg)
- BMI (kg/m²)

Blood pressure and Pulse Rate are measured in a following way:

- Screening
- Day 1 and Week 4 (End of Study)– pre-dose and 30 minutes, 1, 2, 4, 6, 8 and 12 hours post-dose
- Week 1 – Week 3 – pre-dose and 30 minutes, 1, 2 and 3 hours post-dose

BMI is calculated at Screening and End of Study visit using height measured at Screening, and body weight measured at Screening and End of Study visit.

The following summaries will be provided for Vital Signs data, summarised by treatment group:

- Change from baseline table by post-dose time-point of collection for continuous variables
- Shift tables representing changes from Normal/ Low/ High, defined in the Table 5.
- Listings of patients meeting markedly abnormal criteria after the first dose

A plot over time will be presented for all vital signs by treatment group and visit.

17.4.1. Vital Signs Markedly Abnormal Criteria

Markedly abnormal quantitative vital signs measurements will be identified in accordance with the predefined markedly abnormal criteria found in Table 5.

Document: ...\\Verona_Pharma\\RPL554\\BZA48916\\Biostatistics\\Documentation\\SAP\\Verona CO-205 SAP v1.0

Author: [REDACTED] Version Number: V1.0

Version Date: 05DEC2019

Template No.: CS_TP_BS016 Revision 5

Reference: CS_WI_BS005

Effective Date: 01Apr2018

Table 5: Markedly Abnormal Post-Baseline Vital Signs

Vital Sign Parameter	Abnormally Low	Abnormally High
Heart Rate (bpm)	
 - A decrease from Baseline of ≥ 30 - Value ≤ 50 	
 - An increase from Baseline of ≥ 30 - Value ≥ 110
Systolic blood pressure (mmHg)	
 - A decrease from Baseline of ≥ 40 - Value ≤ 90 	
 - An increase from Baseline of ≥ 40 - Value ≥ 180
Diastolic blood pressure (mmHg)	
 - A decrease from Baseline of ≥ 20 - Value ≤ 50 	
 - An increase from Baseline of ≥ 20 - Value ≥ 105
Body weight (kg)	Loss of $\geq 5\%$	Gain of $\geq 5\%$

17.5. Physical Examination

This examination will be performed on major body systems at Screening and at the End of Study visit, and will include the nose, throat, skin, thyroid gland, neurological system, respiratory system, cardiovascular system, abdomen (liver and spleen), lymph nodes and extremities. These will be identified by using the 'Full Physical Examination' page of the eCRF. All these assessments will be recorded as Normal, ANCS or ACS, and ACS results will be described.

The following summaries will be provided for physical examination data, summarised by treatment group:

- Shift tables representing changes from Normal/ ACS/ ANCS
- Listings of patients meeting markedly abnormal criteria after the first dose

17.6. Pharmacokinetics

Pre-dose PK blood samples are collected on Day 1 and at Week 2 and will be used to assess RPL554 steady-state exposure (at Week 2), and tiotropium steady-state exposure prior to and following 14 days of treatment with RPL554 (Day 1 and Week 2).

A correlation plot between PK concentration and change from baseline FEV₁ to pre-dose FEV₁ at Week 2 (morning trough) will be created by treatment group.

The plasma concentrations of tiotropium and RPL554 will be provided by an outside vendor, LGC.

Document: ...\\Verona_Pharma\\RPL554\\BZA48916\\Biostatistics\\Documentation\\SAP\\Verona CO-205 SAP v1.0

Author: [REDACTED] Version Number: V1.0

Version Date: 05DEC2019

Template No.: CS_TP_BS016 Revision 5

Reference: CS_WI_BS005

Effective Date: 01Apr2018

APPENDIX 1. PROGRAMMING CONVENTIONS FOR OUTPUTS

Dates & Times

Depending on data available, dates and times will take the form yyyy-mm-ddThh:mm:ss.

Spelling Format

English US.

Presentation of Treatment Groups

For outputs, treatment groups will be represented as follows and in that order:

Treatment Group	For Tables, Listings and Figures
RPL554 0.375 mg	RPL554 0.375 mg
RPL554 0.75 mg	RPL554 0.75 mg
RPL554 1.5 mg	RPL554 1.5 mg
RPL554 3 mg	RPL554 3 mg
Placebo	Placebo

Decimal Places

The decimal places for this study will use the following rules, unless otherwise stated.

Value = x dp

Mean = x+1 dp

Standard Deviation = x+2 dp

Median = x+1 dp

Q1/Q3 = x+1 dp

Minimum/Maximum = x dp

CI = x+1 dp

For spirometry data we will present outputs with decimal places for value as follows:

- Values in litres = 3dp
- Values in millilitres = 0dp
- Percentage values = 1dp

P-values will be presented to 4dp.

Document: ...\\Verona_Pharma\\RPL554\\BZA48916\\Biostatistics\\Documentation\\SAP\\Verona CO-205 SAP v1.0

Author: [REDACTED] Version Number: V1.0

Version Date: 05DEC2019

Template No.: CS_TP_BS016 Revision 5

Reference: CS_WI_BS005

Effective Date: 01Apr2018

Presentation of Visits

For outputs, visits will be represented as follows and in that order, unless otherwise specified:

Long Name (default)	Short Name
Pre-Screening	Pre-Screening
Screening	Screening
Baseline	Baseline
Day 1	Day 1
Week 1	Week 1
Week 2	Week 2
Week 3	Week 3
Week 4	Week 4
Follow-up	FUP

Listings

All listings will be ordered by the following (unless otherwise indicated in the template):

- Randomized treatment group (or treatment received if it's a safety output)
- Centre-patient ID,
- Treatment day (where applicable),
- Date and time (if applicable),
- For listings where non-randomized patients are included, these will appear in a category after the randomized treatment groups labelled 'Not Randomized'.

Tables

All tables presenting multiple events that map to a SOC and PT will be counted only once, per unique patient, for incidence counts. Events will be presented in descending frequency of SOC and PT (unless otherwise indicated in the template).

Document: ...\\Verona_Pharma\\RPL554\\BZA48916\\Biostatistics\\Documentation\\SAP\\Verona CO-205 SAP v1.0

Author: [REDACTED] Version Number: V1.0

Version Date: 05DEC2019

Template No.: CS_TP_BS016 Revision 5

Reference: CS_WI_BS005

Effective Date: 01Apr2018

APPENDIX 2. PARTIAL DATE CONVENTIONS

Imputed dates will NOT be presented in the listings.

Algorithm for Treatment Emergence of Adverse Events:

START DATE	STOP DATE	ACTION
Known	Known	If start date < study med start date, then not TEAE If start date >= study med start date, then TEAE
	Partial	If start date < study med start date, then not TEAE If start date >= study med start date, then TEAE
	Missing	If start date < study med start date, then not TEAE If start date >= study med start date, then TEAE
<hr/>		
Partial, but known components show that it cannot be on or after study med start date	Known	Not TEAE
	Partial	Not TEAE
	Missing	Not TEAE
<hr/>		
Partial, could be on or after study med start date	Known	If stop date < study med start date, then not TEAE If stop date >= study med start date, then TEAE
	Partial	Impute stop date as latest possible date (i.e. last day of month if day unknown or 31st December if day and month are unknown), then: If stop date < study med start date, then not TEAE If stop date >= study med start date, then TEAE
	Missing	Assumed TEAE
<hr/>		
Missing	Known	If stop date < study med start date, then not TEAE If stop date >= study med start date, then TEAE
	Partial	Impute stop date as latest possible date (i.e. last day

Document: ...\\Verona_Pharma\\RPL554\\BZA48916\\Biostatistics\\Documentation\\SAP\\Verona CO-205 SAP v1.0

Author: [REDACTED]

Version Number: V1.0

Version Date: 05DEC2019

Template No.: CS_TP_BS016 Revision 5

Reference: CS_WI_BS005

Effective Date: 01Apr2018

START DATE	STOP DATE	ACTION
		of month if day unknown or 31st December if day and month are unknown), then: If stop date < study med start date, then not TEAE If stop date >= study med start date, then TEAE
	Missing	Assumed TEAE

Algorithm for Prior / Concomitant Medications:

START DATE	STOP DATE	ACTION
Known	Known	If start date < study med start date and stop date <= study med start date, assign as prior If start date >= study med start date and stop date <= end of treatment, or start date < study med start date and stop date >= study med start date, assign as concomitant If start date > end of treatment, assign as post study
	Partial	If start date < study med start date and stop date <= study med start date, assign as prior If start date >= study med start date and stop date <= end of treatment, or start date < study med start date and stop date >= study med start date, assign as concomitant If start date > end of treatment, assign as post study
	Missing	If stop date is missing could never be assumed a prior medication If start date < end of treatment, assign as concomitant If start date > end of treatment, assign as post treatment

START DATE	STOP DATE	ACTION
Partial	Known	
Impute start date as earliest possible date (i.e. first day of month if day unknown or 1st January if day and month are unknown), then:
 
If start date < study med start date and stop date <= study med start date, assign as prior
 
If start date >= study med start date and stop date <= end of treatment, or start date < study med start date and stop date >= study med start date, assign as concomitant
 
If start date > end of treatment, assign as post study

	Partial	
Impute start date as earliest possible date (i.e. first day of month if day unknown or 1st January if day and month are unknown) and impute stop date as latest possible date (i.e. last day of month if day unknown or 31st December if day and month are unknown), then:
 
If start date < study med start date and stop date <= study med start date, assign as prior
 
If start date >= study med start date and stop date <= end of treatment, or start date < study med start date and stop date >= study med start date, assign as concomitant
 
If start date > end of treatment, assign as post study

	Missing	
Impute start date as earliest possible date (i.e. first day of month if day unknown or 1st January if day and month are unknown), then:
 
If stop date is missing could never be assumed a prior medication
 
If start date < end of treatment, assign as concomitant
 
If start date > end of treatment, assign as post treatment

Missing	Known	
If stop date <= study med start date, assign as prior
 
If stop date > study med start date, assign as concomitant
 
Cannot be assigned as 'post treatment'

Document: ...\\Verona_Pharma\\RPL554\\BZA48916\\Biostatistics\\Documentation\\SAP\\Verona CO-205 SAP v1.0

Author: [REDACTED]

Version Number: V1.0

Version Date: 05DEC2019

Template No.: CS_TP_BS016 Revision 5

Reference: CS_WI_BS005

Effective Date: 01Apr2018

START DATE	STOP DATE	ACTION
	Partial	Impute stop date as latest possible date (i.e. last day of month if day unknown or 31st December if day and month are unknown), then: If stop date <= study med start date, assign as prior If stop date > study med start date, assign as concomitant Cannot be assigned as 'post treatment'
	Missing	Assign as concomitant

Document: ...\\Verona_Pharma\\RPL554\\BZA48916\\Biostatistics\\Documentation\\SAP\\Verona CO-205 SAP v1.0

Author: [REDACTED] Version Number: V1.0

Version Date: 05DEC2019

Template No.: CS_TP_BS016 Revision 5

Reference: CS_WI_BS005

Effective Date: 01Apr2018

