7.4.1.2 Recording and Assessing Adverse Events

All adverse events, whether reported spontaneously by the patient, in response to open questioning on treatment days or observed by the Investigator or his/her staff, will be recorded from informed consent until the telephone follow-up. The start and stop time will be recorded and adverse events will be assessed by the Investigator for the following:

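### The SAP Appendix 2 algorithm has no worsening branch for adverse events known to start before first dose, which contradicts the treatment-emergent definition in SAP 17.1

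*SAP*

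**What the plan says.** SAP 17.1 gives the definition. Besides events that begin after first dose, it counts as TEAE those that "start prior to first dose of study treatment and worsen, based on the investigator's assessment of severity", where the worsening falls on or after first dose. The complementary non-TEAE class is limited to events that "start prior to first dose of study treatment and end prior to first dose of study treatment, or do not worsen". Where emergence cannot be determined, 17.1 defaults to treatment-emergent. It then sends the reader to the appendix: "If any AE records contain only partial dates, these will be handled by imputation, as described in the Appendix 2".

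SAP Appendix 2 contains a table headed as the algorithm for treatment emergence. For a known start date, whether the stop date is known, partial or missing, it says "If start date < study med start date, then not TEAE". For the start-date category "Partial, but known components show that it cannot be on or after study med start date", all three stop-date rows return not TEAE. Where the start date is missing, or partial and possibly on or after dosing, the stop date decides: "If stop date >= study med start date, then TEAE". If the stop date is also missing, the event is assumed to be a TEAE. No row mentions severity.

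Protocol 7.4.1.2 says that AEs "will be recorded from informed consent until the telephone follow-up", so events with a start before dosing are expected in the database.

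**The concern.** One SAP gives two rules for the same event, and they give opposite answers. An event recorded during washout or run-in that is still present at dosing and then becomes more severe is a TEAE under 17.1. With a known start date, it is not a TEAE under Appendix 2.

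The AE summaries listed in 17.1 are all restricted to TEAEs: overall, related, serious, leading to discontinuation, by maximum severity and fatal. Non-TEAEs appear only in listings. A pre-dose event that turned severe or treatment-limiting on study drug could therefore be missing from every summary table, although the SAP's own definition includes it.

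The result also sits oddly with the worst-case default. Appendix 2 counts an event with both dates missing, but excludes one with a documented start and a documented worsening.

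**Working it through.** The plan gives no figure to reproduce here, so the check compares the two rules case by case.

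**Test case.** An AE starts before first dose, continues past it, and worsens in severity on treatment. By 17.1 it is a TEAE, whatever the completeness of its dates. Appendix 2 has four start-date types and three stop-date types (known, partial, missing), so there are 4 × 3 = 12 cells.

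| Start date | Stop-date types | SAP 17.1 | Appendix 2 | Cells in conflict |
|---|---|---|---|---|
| Known, before first dose | 3 | TEAE | not TEAE | 3 |
| Partial, certain to precede first dose | 3 | TEAE | not TEAE | 3 |
| Partial, could be on or after first dose | 3 | TEAE | TEAE | 0 |
| Missing | 3 | TEAE | TEAE | 0 |

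Conflicts: 3 + 3 + 0 + 0 = 6 of 12. These are cells of the table, not a proportion of events. An event with a complete start date before dosing always falls in a conflicting row.

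**Same case without worsening.** Both texts give not TEAE in the first six cells. In the last six, Appendix 2 gives TEAE. That over-counts if the start was in truth before dosing, but it follows the worst-case default in 17.1 and is not a further conflict.

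**Can the affected class occur?** Consent is taken at Visit 0 (Protocol 6.2). Protocol section 6 places Visit 0 between 2 and 28 days before Visit 1, and Visit 1 at 14 ± 1 days before first dose, that is 13 to 15 days.
- Shortest collection period before first dose: 2 + 13 = 15 days.
- Longest: 28 + 15 = 43 days.

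This period includes the washout of prior COPD medication and the tiotropium run-in. It shows that the class is not empty by design. It does not show how many events fall in it.

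**After the fix.** With the worsening condition added to the six conflicting rows, the conflicts fall from 6 of 12 to 0 of 12.

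**The case against.** The best defence is that 17.1 is the definition and Appendix 2 only supports it. The appendix is titled as a set of partial-date conventions, and 17.1 refers to it only for partial dates. On that view a programmer would apply 17.1 to complete records and no event would be lost. This stands in part: nothing in the SAP gives Appendix 2 precedence, so a reader who infers that it is certain to be programmed goes further than the text. But the table rules explicitly on fully known dates, and its partial-date rows for starts certain to precede dosing conflict with 17.1 as well. The title does not remove the contradiction.

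Second, a worsening may be entered as a new AE. Protocol 7.4.1.1 includes worsening during the study in its definition of an AE, and conditions active at Screening are recorded as medical history (Protocol 7.1.2). If a worsening gets its own record, dated from its onset, it is a TEAE under both texts. This stands, and it narrows the exposed class to pre-dose AEs that worsen within the same record. The documents do not say which way sites must record it.

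Third, the consequence is bounded. Non-TEAEs stay in the listings, SAP section 17 plans no between-group comparisons of safety data unless a section specifies one, and no efficacy result is touched. All of this stands.

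A reader might also fault Appendix 2 for counting every AE that starts on the date of first dose, including one noted before the dose at Visit 2. The documents do not support that. SAP 6.2 states that AEs commencing on the reference start date are post-baseline. The date comparison in Appendix 2 implements this, and it errs toward inclusion.

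**Conclusion.** The contradiction is real and is plain from the text. In the rows for start dates known or certain to precede first dose, Appendix 2 omits the worsening limb of 17.1, and the two texts disagree in 6 of 12 date patterns.

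The effect on the tables depends on two things that the documents leave open: that Appendix 2 is what is programmed, and that the worsening stays within the original AE record. If both hold, these events drop out of the TEAE summaries and remain only in listings.

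Two stronger conclusions are tempting and do not follow. One is that every AE starting before first dose is excluded: events with a missing or ambiguous start can still be TEAEs. The other is that all worsened pre-dose events are lost: that restates the rule for one set of rows and does not measure the effect. The number of events cannot be computed, because the documents give neither the rate of AEs before dosing nor the share that later worsen.

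This should be corrected before unblinding. It is a consistency error in the rule behind the AE summary tables and not a threat to the primary analysis.

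**What to change.** 1. In Appendix 2, change the three known-start rows and the three rows for partial starts certain to precede dosing to: not TEAE unless severity worsens on or after first dose, then TEAE. Alternatively, state in 17.1 and Appendix 2 that the 17.1 definition prevails.
2. State how an on-treatment increase in severity is identified, for example as a new AE record dated from the worsening. Protocol 7.4.1.2 describes start and stop times and a severity assessment, but no date of severity change. Without such a rule the added condition may have nothing to work on.
3. In 17.1, align the wording for newly starting events to on or after first dose, so that it agrees with SAP 6.2 and Appendix 2. No start-time rule is needed for events on the day of first dose.

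Items 1 and 3 cost a few lines of SAP text and a small change to the program. The cost of item 2 depends on what the case report form already captures, which the documents do not show. If it holds no date of severity change, data management would need a recording convention and a review of pre-dose AEs still ongoing at first dose.
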